### **Description of the visit**

A single visit per patient will be carried out for the purposes of this study, coinciding with the study recruitment visit.

For a period of one month, each investigator must identify patients with cancer pain being treated with opioids who attend consultations in in Medical Oncology, Hematology, Radiotherapeutic Oncology Departments, Pain Units and Palliative Care Units, using the patient's medical history and the Davies diagnostic algorithm [3] to confirm the presence of breakthrough pain.

Information relating to the prevalence of breakthrough pain will be collected in the corresponding section of the CRF, detailing for each patient whether he/she has pain, whether he/she has breakthrough pain, age, sex, Karnofsky PS, tumour type and stage.

From those patients who report breakthrough pain, the first two patients each day who meet the inclusion criteria and give their informed consent will be recruited, until reaching the indicated sample size of 10 patients in Medical Oncology, Hematology, Radiotherapeutic Oncology and Palliative Care Departments and 5 patients in Pain Units, until a total of 529 is reached.

If, following the recruitment period planned in the protocol (maximum 3 months), the expected number of patients for the characterisation of breakthrough pain has not been reached, recruitment will be continued competitively within each specialty (120 patients included in each specialty except 60 patients in hematology), until 529 patients have been recruited.

The information will be recorded on the Case Report Forms (CRFs) designed for this purpose. All the information will be filled in by the investigating physician using the data obtained during the study visit or by checking the patient's medical records when necessary.

The following information will be collected during the visit:

- Visit date
- Demographic data (age, sex, weight, height)
- Characteristics of the cancer (type, stage, treatments the patient has received for the underlying tumour: chemotherapy, radiotherapy, surgery, etc.) as well as whether he/she is currently receiving treatment for the tumour.
- Comorbidities
- Adverse events associated with the cancer treatment or sequelae of the tumour: (mucositis, xerostomia, nausea, vomiting, dysphagia, dyspnoea, peripheral neuropathy, tiredness/weakness, constipation, diarrhoea, sleep disorders, other)
- Clinical assessment of the breakthrough pain:
  - Alberta Breakthrough Pain Assessment Tool for the assessment of breakthrough pain in cancer patients
  - Brief Pain Inventory (BPI)

- Numerical Rating Scale (NRS) for the assessment of pain intensity
- Quality of life assessment:
  - SF-12 Questionnaire
  - Karnofsky performance status

Using an anatomical drawing or doll, the exact location in which the patient presents the breakthrough cancer pain crisis will be identified, determining whether one or several breakthrough pains are involved.

A series of graphs illustrating various profiles for the behaviour of breakthrough pain will then be used, in order to determine which type(s) of breakthrough pain each patient recruited to the study presents.

[figure not shown]
The following graphs will be used:

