**BCP type IV graph:**

This graph represents BCP that starts gradually, reaches a maximum peak and is maintained for a period, before gradually decreasing.

The fundamental exposure factor in this study is patients with cancer who attend consultation at in Medical Oncology, Hematology, Radiotherapeutic Oncology Departments, Pain Units and Palliative Care Units with cancer pain controlled with opioids. Using patients' medical history and the Davies diagnostic algorithm [3], the investigator will confirm the presence of breakthrough pain. Those patients who agree to participate in the study to characterise breakthrough pain by signing the informed consent will be questioned on the other study variables and asked to complete the corresponding questionnaires.

All study data will be collected during the visit in which the patient signs the informed consent.

The data detailed below will be collected in relation to the study objectives:

- The primary assessment variable is the prevalence of breakthrough pain in patients with cancer pain controlled with opioids who attend consultations in Medical Oncology, Hematology and Radiotherapeutic Oncology Departments or Pain and Palliative Care Units for any reason.

Breakthrough pain is understood as the temporary exacerbation of pain occurring either spontaneously or in relation to a specific, predictable or unpredictable trigger in spite of relatively stable and adequately controlled baseline pain.

For a period of one month, each investigator will identify patients with cancer pain being treated with opioids who attend consultations, using the patient's medical history and the Davies diagnostic algorithm [3] to confirm the presence of breakthrough pain.

The investigator will continue collecting information from patients to estimate the prevalence for a month, regardless of whether the investigator recruited the 10 assigned patients (5 in pain units) for the characterization of breakthrough pain before.

- The prevalence of breakthrough pain in patients with cancer who attend consultations in Medical Oncology, Hematology, Radiotherapeutic Oncology Departments, Pain Units and Palliative Care Units for any reason over one month will also be determined.

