- In order to determine the incidence of breakthrough pain in patients with cancer pain controlled with opioids, the investigator will indicate on the prevalence data sheet whether the breakthrough pain has been diagnosed during the current visit or was diagnosed at an earlier date. Cases of breakthrough pain diagnosed during 1 month will be used to calculate its incidence.
- The incidence of breakthrough pain in patients with cancer who attend consultations in in Medical Oncology, Hematology, Radiotherapeutic Oncology Departments, Pain Units and Palliative Care Units for any reason over one month will also be determined.
- During the same visit, demographic data and information relating to the characteristics of the cancer will be collected from all patients with breakthrough cancer pain who agree to participate in the study.
- The characterisation of breakthrough pain in patients with cancer pain will be carried out using the information collected in the tools used for the clinical assessment of the breakthrough pain:
  - o Alberta Breakthrough Pain Tool
  - o BPI questionnaire and
  - o Numerical Rating Scale for the assessment of pain intensity
- To assess the quality of life of patients with cancer pain, we will use:
  - o SF-12 Questionnaire

- Karnofsky performance status

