### 5.1. Primary objective analysis

In the prevalence study the following variables will be collected:

- Patient with cancer pain: yes/no
- Breakthrough cancer pain: yes/no
- Diagnostic of BCP: Previously diagnosed; Diagnosed during the visit (according Davies algorithm)
- Date of visit.
- Age.
- Gender.
- Karnofsky PS (0 to 100).
- Type of tumour: head and neck, colorectal, esophagus, stomach, liver, leukemia, lymphoma, breast, multiple myeloma, bone and muscular, ovarian, pancreas, prostate, lung, kidney, central nervous system, testicle, uterus, bladder and other).
- Stage (I-IV).

The prevalence of breakthrough cancer pain and corresponding 95% confidence interval (95%CI) will be calculated as the percentage of subjects presenting breakthrough pain among patients with cancer pain controlled with opioids, collected by all investigators over one month.

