#### Formula:

Prevalence of breakthrough cancer pain (%) = [Number of patients with breakthrough cancer pain / total number of patients registered with cancer pain] x 100.

The estimated annual prevalence will be calculated relative to the population of cancer patients with or without pain seen over one month.

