## 5.2. Secondary objective analysis

To describe the population the following variables will be analyzed:

- o Patient with cancer pain: yes/no
- o Breakthrough cancer pain: yes/no
- o Diagnostic of BCP: Previously diagnosed; Diagnosed during the visit (according Davies algorithm)
- o Date of visit.
- o Age.
- o Gender.
- o Karnofsky PS (0 to 100).
- o Type of tumour: head and neck, colorectal, esophagus, stomach, liver, leukemia, lymphoma, breast, multiple myeloma, bone and muscular, ovarian, pancreas, prostate, lung, kidney, central nervous system, testicle, uterus, bladder and other).
- o Stage (I-IV).

In the prevalence study we will calculate the following results:

- The prevalence of breakthrough cancer pain (primary objective) according to gender (separately for men and women) and corresponding 95%CI.
- The prevalence of breakthrough cancer pain (primary objective) according to age (separately for the following categories: < 70years; ≥ 70years) and corresponding 95%CI.
- The prevalence of breakthrough cancer pain (primary objective) according to specialty (separately for the following categories: Medical Oncology, Hematology, Radiotherapeutic Oncology Departments, Pain Units and Palliative Care Units) and corresponding 95%CI.
- The prevalence of breakthrough cancer pain (primary objective) according to Karnofsky PS (separately for all categories of PS) and corresponding 95%CI.
- The prevalence of breakthrough cancer pain (primary objective) according to type of tumour (separately for all categories of type of tumour) and corresponding 95%CI.
- The prevalence of breakthrough cancer pain (primary objective) according to Stage (separately for I, II, III and IV) and corresponding 95%CI.
- The prevalence of new cases of breakthrough cancer pain and corresponding 95%CI.

Formula:

Prevalence of new cases of breakthrough cancer pain (%) = [Number of patients with breakthrough cancer pain that were diagnosed during the visit / total number of patients registered with cancer pain] x 100.

- The prevalence of breakthrough cancer pain over the total of patients with cancer and corresponding 95%CI.

Formula:

Prevalence of breakthrough cancer pain (%) = [Number of patients with breakthrough cancer pain / total number of patients registered with cancer] x 100.

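### The listed prevalence-register fields do not identify the opioid-controlled denominator that the primary variable needs

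*Protocol*

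**What the plan says.** **Population for the primary variable.** Protocol Section 7 (under the BCP type IV graph heading) states: "The primary assessment variable is the prevalence of breakthrough pain in patients with cancer pain controlled with opioids who attend consultations". The protocol Summary and Section 10.1 use the same denominator. The text of SAP 5.1 (Primary objective analysis) describes the estimate as the "percentage of subjects presenting breakthrough pain among patients with cancer pain controlled with opioids, collected by all investigators over one month".

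**Formulas.** The SAP 5.1 formula has no opioid or control condition: "Number of patients with breakthrough cancer pain / total number of patients registered with cancer pain] x 100". SAP 5.2 adds a prevalence over all cancer patients: "Number of patients with breakthrough cancer pain / total number of patients registered with cancer] x 100". The formal primary objective (Protocol Section 3, SAP 3.5) also refers to all cancer outpatients, whether or not they have pain.

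**Fields recorded.** Under Description of the visit, the protocol says that the prevalence section of the CRF is completed "detailing for each patient whether he/she has pain, whether he/she has breakthrough pain, age, sex, Karnofsky PS, tumour type and stage". Section 7 later adds that "the investigator will indicate on the prevalence data sheet whether the breakthrough pain has been diagnosed during the current visit" or earlier. The lists in SAP 5.1 and 5.2 are the fullest. They contain "Patient with cancer pain: yes/no", breakthrough pain yes/no, new or previous diagnosis, visit date, age, gender, Karnofsky PS, tumour type and stage.

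**Analysis set.** SAP 4.1 takes everyone on the prevalence form and applies no restriction by opioid use or pain control. The criterion of adequate control on opioids (Protocol 6.3, SAP 3.7) selects patients for the characterisation part.

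**The concern.** A prevalence among opioid-controlled patients needs two facts about every patient with cancer pain: whether an opioid is being taken, and whether baseline pain is controlled. For patients with breakthrough pain, control follows from the protocol's own definition of the condition. For patients with pain but no breakthrough pain, no listed field supplies either fact, and these are the patients who complete the denominator.

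If the SAP formula is applied to a register of all attenders, its result answers a different question from the one that its label states. Rewording the formula would not help, because there is no listed field to filter on. The estimates by specialty (Protocol 10.1, SAP 5.2) are also exposed: if the opioid-controlled share of pain patients differs between, say, Pain Units and Hematology, part of any difference in prevalence reflects that share.

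**Working it through.** **1. Needed against listed.**

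| Item | Protocol Section 7 | SAP 5.1 and 5.2 |
|---|---|---|
| Cancer pain yes/no | listed | listed |
| Breakthrough pain yes/no | listed | listed |
| New or previous diagnosis | listed | listed |
| Opioid treatment | not listed | not listed |
| Baseline pain controlled | not listed | not listed |

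**2. Who is registered.** The documents support two readings.

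| Prevalence | A: every cancer attender (Protocol 6.3) | B: only cancer pain treated with opioids (Protocol 7, 10.1) |
|---|---|---|
| Over all cancer patients | computable | only if the CRF page named in Protocol 10.1 holds a separate count |
| Over all patients with cancer pain | computable | not computable; the pain field is constant |
| Over opioid-treated pain | not identifiable | computable |
| Over opioid-controlled pain | not identifiable | control unknown for non-cases |

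Under B the opening of Section 7 restricts the patients to third-step opioids, while later text says opioids. The listed fields could not show which was applied, and the passages need to be reconciled.

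**3. The plan's own figure.** Protocol 10.3 gives 66 × 200 = 13,200 patients, 50% prevalence and ±1% precision. The 95% half-width is 1.96 × √(0.5 × 0.5 / 13,200) = 0.0085, or ±0.85 points, consistent with ±1. Exactly ±1 point needs 1.96² × 0.25 / 0.01² = 9,604 patients. The figure reproduces and serves here as a yardstick.

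**4. Size and direction.** Let f be the opioid-controlled share of registered pain patients, P the prevalence in that group, and P₀ the proportion of the other pain patients recorded as cases. The SAP 5.1 formula returns

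P × f + P₀ × (1 − f),

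which differs from P by (1 − f) × (P − P₀). It understates P whenever P₀ is below P. If no case lies outside the group, P₀ = 0 and the result is P × f. With P = 0.50 and f from 0.4 to 0.9, all assumed:

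| f | Formula returns | Shortfall (points) |
|---|---|---|
| 0.4 | 20% | 30 |
| 0.5 | 25% | 25 |
| 0.6 | 30% | 20 |
| 0.7 | 35% | 15 |
| 0.8 | 40% | 10 |
| 0.9 | 45% | 5 |

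These values illustrate reading A. Under B, f reflects control alone, so it may be higher and the shortfall smaller.

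**5. Specialties.** On the same assumptions, two specialties that share a true 50% but have f = 0.9 and f = 0.5 would appear as 45% and 25%.

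**6. Precision in the named group.** If the 13,200 are all attenders, the outpatient pain range of 18% to 62% in the protocol Introduction gives 13,200 × 0.18 = 2,376 to 13,200 × 0.62 = 8,184 pain patients. With f from 0.4 to 0.9, the opioid-controlled group has 2,376 × 0.4 ≈ 950 to 8,184 × 0.9 ≈ 7,366 patients. At 50% the half-width is 1.96 × 0.5 / √950 ≈ 3.2 points down to 1.96 × 0.5 / √7,366 ≈ 1.1 points.

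**The case against.** **The form may carry the meaning.** The protocol's field list follows directly after an instruction to identify opioid-treated cancer pain. In the SAP, the formula follows directly after text that names the opioid-controlled group. Cancer pain *yes* may therefore be shorthand for that group. If the CRF defines it so and every attender is registered, both prevalences can be computed. No passage states that definition, so this shows ambiguity but does not settle it.

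**The all-cancer count may exist separately.** Protocol 10.1 says that each investigator collects the number of cancer patients on the relevant CRF page, which can be read as an aggregate count. That would rescue the all-cancer prevalence under reading B. A reader might infer that no reading gives both planned prevalences; with these two possibilities open, the documents do not support so strong a statement. A separate count would still leave baseline control unrecorded for non-cases.

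**The formal objective is not affected in the same way.** A reader might conclude that the study cannot deliver its primary estimate at all. The primary objective in Protocol Section 3 and SAP 3.5 is set in all cancer outpatients, and the listed fields deliver it if every attender is registered. Only the opioid-controlled version is affected. That version is nevertheless what the protocol calls the primary variable and what the SAP text calls the primary analysis.

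**Conclusion.** The point holds for the fields that the plan lists. They do not identify the opioid-controlled denominator, the prevalence population applies no filter, and the SAP formula substitutes all registered cancer pain. This should be corrected; relabelling alone is enough where the data can no longer be completed.

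Two stronger inferences are not supported:

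- *The items were never collected.* The CRF is not in the documents, and the protocol's main field list is visibly incomplete, since other places add items. Medical records are also an allowed source (Description of the visit), so a gap need not be permanent.
- *The estimate is 5 to 30 points too low.* The documents do not give f. Protocol 10.3 applies its 50% to patients generally and does not tie it to opioid-controlled pain. P × f also requires that no case lies outside the group. The definition in the Introduction and Section 7 requires controlled baseline pain, but only the description cited in the Introduction mentions opioid treatment. If cases without opioids are recorded, the shortfall shrinks.

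The direction, dilution, is therefore probable. The size is illustrative, and the distortion between specialties depends on f differing among them.

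**What to change.** **Change.** Add two fields to the prevalence form, to Protocol Section 7 and to the variable lists in SAP 5.1 and 5.2: *baseline cancer pain treated with opioids (yes/no)* and *baseline pain adequately controlled (yes/no)*. Both should be judged as for the existing inclusion criterion in Protocol 6.3. State that every cancer attender is registered. Compute the opioid-controlled prevalence on patients with both fields *yes*, and the all-cancer prevalence on everyone. If the CRF already holds these items or defines cancer pain that way, state this in the SAP and give the filter.

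**Months already collected.** Complete the two fields from medical records where feasible. Otherwise report the SAP 5.1 result only as prevalence among the patients registered with cancer pain.

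**Cost.** A small extra entry for each registered patient, including pain patients without breakthrough pain, for whom the investigator might not otherwise judge control. Some variation between sites in judging control will remain. Protocol Section 10 provides for a revised SAP before data collection ends. A change to the protocol's methods would go back to the ethics committee under Section 5.1.

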**BCP type I graph:**

This graph represents BCP of short duration and high intensity, that begins and ends suddenly.

intensity

[figure not shown]
**BCP type II graph:**

This graph represents BCP of long duration and moderate-high intensity, that begins and ends gradually.

**BCP type III graph:**

This graph represents BCP with successive pain peaks of gradually decreasing intensity.

**BCP type IV graph:**

This graph represents BCP that starts gradually, reaches a maximum peak and is maintained for a period, before gradually decreasing.

The fundamental exposure factor in this study is patients with cancer who attend consultation at in Medical Oncology, Hematology, Radiotherapeutic Oncology Departments, Pain Units and Palliative Care Units with cancer pain controlled with opioids. Using patients' medical history and the Davies diagnostic algorithm [3], the investigator will confirm the presence of breakthrough pain. Those patients who agree to participate in the study to characterise breakthrough pain by signing the informed consent will be questioned on the other study variables and asked to complete the corresponding questionnaires.

All study data will be collected during the visit in which the patient signs the informed consent.

The data detailed below will be collected in relation to the study objectives:

- The primary assessment variable is the prevalence of breakthrough pain in patients with cancer pain controlled with opioids who attend consultations in Medical Oncology, Hematology and Radiotherapeutic Oncology Departments or Pain and Palliative Care Units for any reason.

Breakthrough pain is understood as the temporary exacerbation of pain occurring either spontaneously or in relation to a specific, predictable or unpredictable trigger in spite of relatively stable and adequately controlled baseline pain.

For a period of one month, each investigator will identify patients with cancer pain being treated with opioids who attend consultations, using the patient's medical history and the Davies diagnostic algorithm [3] to confirm the presence of breakthrough pain.

The investigator will continue collecting information from patients to estimate the prevalence for a month, regardless of whether the investigator recruited the 10 assigned patients (5 in pain units) for the characterization of breakthrough pain before.

- The prevalence of breakthrough pain in patients with cancer who attend consultations in Medical Oncology, Hematology, Radiotherapeutic Oncology Departments, Pain Units and Palliative Care Units for any reason over one month will also be determined.
- In order to determine the incidence of breakthrough pain in patients with cancer pain controlled with opioids, the investigator will indicate on the prevalence data sheet whether the breakthrough pain has been diagnosed during the current visit or was diagnosed at an earlier date. Cases of breakthrough pain diagnosed during 1 month will be used to calculate its incidence.
- The incidence of breakthrough pain in patients with cancer who attend consultations in in Medical Oncology, Hematology, Radiotherapeutic Oncology Departments, Pain Units and Palliative Care Units for any reason over one month will also be determined.
- During the same visit, demographic data and information relating to the characteristics of the cancer will be collected from all patients with breakthrough cancer pain who agree to participate in the study.
- The characterisation of breakthrough pain in patients with cancer pain will be carried out using the information collected in the tools used for the clinical assessment of the breakthrough pain:
  - o Alberta Breakthrough Pain Tool
  - o BPI questionnaire and
  - o Numerical Rating Scale for the assessment of pain intensity
- To assess the quality of life of patients with cancer pain, we will use:
  - o SF-12 Questionnaire

- Karnofsky performance status

## **8 Safety Reporting**

### **8.1 Definitions**

#### **Adverse Event**

An adverse event (AE) is any untoward medical occurrence in a subject administered a medicinal product and which does not necessarily have to have a causal relationship with this treatment. An adverse event can therefore be any unfavourable and unintended sign (e.g. an abnormal laboratory finding), symptom, a new disease or worsening in severity or frequency of a concomitant disease temporally associated with the use of a medicinal product, whether or not considered related to the medicinal product.

